6.10.2. Secondary Efficacy Analyses

Table AMBU.6.4 includes the description and derivation of the efficacy/health outcomes measures and endpoints. The analysis of secondary efficacy/health outcomes measures and endpoints is described in Table AMBU.6.5.

6.10.3. Exploratory Efficacy Analyses

The analysis of predetermined exploratory efficacy/health outcomes measures and endpoints is described in Table AMBU.6.6. Other exploratory analyses may be added as deemed appropriate.

6.11. Health Outcomes Analyses

6.11.1. Health Care Utilization

Hospitalization is recorded in the Healthcare Visit eCRF. Categories of healthcare visits include: acute care, emergency room, immediate care, intensive care, physical rehabilitation, outpatient office/clinic, professional healthcare at home, infusion center, and other. Ulcerative colitis-related hospitalizations may be determined from the related AE eCRF. Summary statistics will be reported for the number and percentage of patients with UC-related hospitalization overall and within each category by weight/treatment dose group.

Ulcerative colitis-related surgery is recorded in the Surgical Procedures eCRF. Types of surgery include proctocolectomy, total colectomy, partial colectomy, colostomy, ileoanal anastomosis, and ileostomy. As with hospitalizations, summary statistics will be reported for the number and percentage of patients with any surgery, a colectomy surgery (ie, proctocolectomy, total colectomy, partial colectomy) and within each surgery category by weight/treatment dose group.

6.12. Pharmacokinetic/Pharmacodynamic Methods

The bioanalytical and PK/PD analyses will be conducted by the PK/PD and Pharmacometrics group at Eli Lilly. Pharmacokinetic/PD analyses to address primary objectives of this study will be described by Lilly in a separate PK/PD analysis plan.

6.13. Safety Analyses

The planned analyses of safety data will be performed with an intent to maintain consistency with compound level safety standards. These standards are based on internal standards which were informed by Clinical Data Interchange Standards Consortium standards, regulatory guidance (eg, Food and Drug Administration Clinical Review Template), and cross-industry standardization efforts (eg, Pharmaceutical Users Software Exchange [PhUSE] white papers from the Standard Analyses and Code Sharing Working Group provided in the PhUSE Computational Science Deliverables Catalog [PhUSE (WWW)).

Analyses of safety data will be based on the Safety population as defined in Table AMBU.6.1. The analysis treatment periods of interest will be the Induction and the combined Induction and Maintenance period; the associated weight/treatment dose groups for each period are described

in Table AMBU.6.2. Unless otherwise stated, safety data collected during the follow-up periods for patients that do not enroll in the long-term extension Study I6T-MC-AMAZ will be listed.

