Upon completion of the maintenance period (Week 52), all patients will have the option to enter the 3-year long-term extension Study I6T-MC-AMAZ (AMAZ) or enter the post-treatment follow-up period (12 weeks following SC administration). With sponsor approval, additional dosing at Week 52 and unscheduled visits (UV) beyond Week 52 may occur as needed for patients eligible to enroll in Study AMAZ where the clinical trial site is not yet open. Patients must have completed all procedures at Visit 16 and additional dosing should occur at 4-week intervals (±7 days) from the prior dose. Patients who discontinue while receiving IV dosing will undergo procedures for early termination of the study drug, including post-treatment follow-up for 16 weeks as described in the Schedule of Activities (Section 2).

Figure AMBU.1 illustrates the study design

Study governance considerations are described in detail in Appendix 3.

[figure not shown]

Figure AMBU.1. Illustration of study design for clinical protocol I6T-MC-AMBU.

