8.1. Discontinuation from Study Drug

8.1.1. Permanent Discontinuation from Study Drug

Study drug may be permanently discontinued during the study. Patients who discontinue study drug early will undergo early termination procedures, which include an ETV and post-treatment follow-up visits.

The investigator will also complete any AE reporting and follow-up that may be required (if applicable, see Section 9.2).

If a patient's study drug is discontinued before the end of the study, the patient should complete the ETV and post-treatment follow-up period as follows:

- Patients who discontinue investigational product during [redacted] will return for post-treatment follow-up visits (Visits 801 and 802) [redacted] after the end-of-treatment visit.
- Patients who discontinue study drug [redacted] will return for post-treatment follow-up visits (Visits 801 and 802) [redacted] after the end-of-treatment visit.

[figure not shown]
Possible reasons leading to permanent discontinuation of investigational product include the following (list is not exhaustive):

Patient Decision

- The patient or the patient's designee, for example, parents or legal guardian, requests to discontinue investigational product.

[redacted]

[redacted]

Disease Worsening

- The patient requires rescue therapy for exacerbation of UC at doses higher than those specified in the “dose stabilization” inclusion criterion (for example, prednisone **CCI** Inclusion Criterion [9]), or with medications specified in the “prohibited medications” exclusion criterion (for example, IV corticosteroids, infliximab, or IV cyclosporine; Exclusion Criterion [19]) (see also [Appendix 5](#)).

Safety Criteria for Study Drug Discontinuation

- The patient has a diagnosis of any of the following during the study:
 - Cancer other than squamous cell or basal cell carcinoma of the skin
 - Polypoid or non-polypoid dysplasia that is endoscopically visible or invisible
 - Active TB (see Section [9.4.5.2](#))
 - HIV/AIDS
 - Hepatitis B or development of detectable HBV DNA (see Section [9.4.5.4](#))
 - Hepatitis C or development of detectable HCV RNA (see Section [9.4.5.5](#)).
- The patient requires a colectomy during the study.
- The patient has a systemic hypersensitivity event or anaphylaxis to mirikizumab (Section [7.8.3.2](#)). Study drug should be discontinued after a systemic hypersensitivity event or anaphylaxis.

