10.3.4. Safety Analyses

Safety data will be summarized by dose. Safety and tolerability including but not limited to AEs, infections, injection site reactions, clinical chemistry, hematology, immunogenicity, tolerability and acceptability of SC injection volumes of CCI, and questionnaires to assess the existence and severity of depression will be assessed.

For AEs, the number of treatment-emergent adverse events (TEAEs), as well as the number and percentage of patients who reported at least 1 TEAE will be summarized using Medical Dictionary for Regulatory Activities (MedDRA) for each system organ class and preferred term.

Serious adverse events (including deaths), treatment-emergent AESIs, and AEs that lead to treatment discontinuation will also be summarized using MedDRA for each system organ class and preferred term.

For laboratory analytes and vital signs, treatment-emergent abnormal shifts to low/high will be presented.

Summary tables or listings for [CCI] will be produced as needed.

Immunization history will be recorded at baseline, and any unexpected outcomes or effects related to standard of care vaccination during the study will be summarized.

Further analyses may be performed as deemed appropriate and will be detailed in the SAP.

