6.6. Patient Disposition

Screen failures and reason for screen failure will be summarized. The treatment disposition and study disposition will be summarized for the modified intent-to-treat (mITT) population. Disposition summaries will be by weight/treatment dose group and overall. Summaries will also include reason for discontinuation from the study tabulated by weight/treatment group for all patients.

Additionally, a listing of all patients who are enrolled and received at least one dose of miri (ie, the mITT population) and discontinued from study treatment during any period from the study

will be provided, and the timing of discontinuing the study will be reported. If known, a reason for their discontinuation will be given.

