6.13.2. Adverse Events

A treatment-emergent adverse event (TEAE) is defined as an event that first occurred or worsened in severity after baseline. The MedDRA Lowest Level Term (LLT) will be used in the treatment-emergent computation. The maximum severity for each LLT during the baseline period will be used as baseline. For events with a missing severity during the baseline period, it will be treated as 'mild' in severity for determining treatment-emergence. Events with a missing severity during the postbaseline periods will be treated as 'severe' and treatment-emergence will be determined by comparing to baseline severity. For events occurring on the day of first taking study medication, the start times of the study treatment and AE will be used to determine whether the event was pre- versus post-treatment. If start time for the AE is missing, it will be assumed to have started in the postbaseline period.

Summary tables of AEs to include the following:

- overview of AEs
- summary of TEAE Preferred Terms (PTs) by decreasing frequency
- summary of TEAE PTs by decreasing frequency within System Organ Class (SOC)
- summary of TEAE PTs by maximum severity by decreasing frequency within SOC
- summary of serious adverse event (SAE) PTs by decreasing frequency
- summary of AEs leading to study discontinuation, and

• listing of SAEs.

Summary tables will include the number and percentage of patients reporting an event. For events that are gender-specific (as defined by MedDRA), the number of participants at risk will include only patients from the given gender

The baseline period and postbaseline periods will be defined as follows:

- the baseline period is the Screening period, and
- the postbaseline periods will be a) the Induction period and b) the combined Induction and Maintenance period (see Table AMBU.6.2).

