6.13.3. Deaths, Other Serious Adverse Events, and Other Notable Adverse Events

The number and percentage of patients who reported a SAE (including those resulting in death) during the safety analysis treatment periods will be summarized by weight/treatment dose group using MedDRA PT nested within SOC. Events will be ordered by decreasing frequency within SOC. A listing of SAEs will be provided.

The number and percentage of patients who permanently discontinued from study treatment due to an AE (including AEs that led to death) during each period will be summarized by weight/treatment dose group using MedDRA PT nested within SOC. Events will be ordered by decreasing frequency within SOC.

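### SAE and death counts by dose group in the study report stop at the end of treatment, so a new SAE or death in the 12- to 16-week follow-up is listed but not counted

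*SAP*

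**What the plan says.** **SAP.** Section 6.13 names two analysis periods for safety, Induction and combined Induction and Maintenance. For what comes after, unless stated otherwise, "safety data collected during the follow-up periods for patients that do not enroll in the long-term extension Study I6T-MC-AMAZ will be listed". Section 6.13.2 repeats the limit for the adverse event tables: "the postbaseline periods will be a) the Induction period and b) the combined Induction and Maintenance period". Section 6.13.3 reports the number and percentage of patients with an SAE, fatal ones included, and restricts it in the same way: events "during the safety analysis treatment periods will be summarized by weight/treatment dose group". Footnote a to Table AMBU.6.1 ties the safety population to the same two periods. Sections 6.13.2 and 6.13.3 also promise a listing of SAEs.

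**Protocol.** Follow-up is planned observation. Section 8.1.1 says: "Patients who discontinue study drug early will undergo early termination procedures, which include an ETV and post-treatment follow-up visits". Section 5.1 gives 12 weeks of follow-up after SC dosing. For children who stop during IV dosing it describes early termination procedures, "including post-treatment follow-up for 16 weeks as described in the Schedule of Activities". The Schedule of Activities marks adverse event review at both follow-up visits (801 and 802). On reporting, Section 10.3.4 says: "Serious adverse events (including deaths), treatment-emergent AESIs, and AEs that lead to treatment discontinuation will also be summarized using MedDRA". That sentence names no period, although Section 10.3.1 organizes the safety analyses by induction and maintenance.

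**The concern.** The study collects adverse events for three to four months after the last treatment visit in every child who stops early and in every completer who does not move to Study AMAZ. The CSR tables that a reader will use to compare SAEs and deaths across dose groups end before that window opens. A serious infection that begins six weeks after an early termination visit would be in a listing and absent from the SAE percentage for its dose group.

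The count can therefore understate the SAEs and deaths recorded in the study. To correct it, a reader of the CSR would have to go through the listing and add cases up by group. In proportion to time observed, the effect is largest for children who stop early, some of whom stop because of an adverse event.

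**Working it through.** The plan states no figure to reproduce on this point. The check is a reading of the text, followed by simple arithmetic on the planned durations.

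**Step 1. Which CSR output counts a follow-up SAE?**

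| Output | Covers follow-up? |
|---|---|
| TEAE tables (SAP 6.13.2) | No; two treatment periods only |
| SAE and death count by dose group (SAP 6.13.3) | No; treatment periods only |
| Listings (SAP 6.13, 6.13.2, 6.13.3) | Yes, but no number or percentage by group |
| Disposition (SAP 6.6) | In part: a death may appear as a reason for leaving the study |
| Hospitalization and surgery (SAP 6.11.1) | In part: UC-related only, and the text names no period |

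The two partial outputs are worded as follows. Disposition: "Summaries will also include reason for discontinuation from the study tabulated by weight/treatment group for all patients". Hospitalization: "number and percentage of patients with UC-related hospitalization overall and within each category by weight/treatment dose group". A serious infection unrelated to UC is in neither unless it ends study participation.

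**Step 2. The registry output.** SAP 6.18 plans a summary of serious events by treatment/weight group. It treats an event as serious regardless of whether it is treatment-emergent, and it sets no period limit. It may therefore count a follow-up SAE that the 6.13.3 table leaves out. The same section says adverse event reporting is consistent with the CSR. If follow-up SAEs are included, the two counts can differ.

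**Step 3. Share of observed time outside the SAE count.**

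Inputs: follow-up of 16 weeks after IV and 12 weeks after SC (Protocol 5.1); dosing every 4 weeks. Assumption: the treatment period closes at the early termination visit, or at Week 52 for a completer, and the last dose was 4 weeks before that visit.

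The anchor of the follow-up clock is not fully visible. Protocol 5.1 counts the 12 weeks from SC administration, while Protocol 8.1.1 times the follow-up visits from the end-of-treatment visit, with the intervals redacted. Both are shown.

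Let T be weeks to the last treatment visit and F the nominal follow-up.
- From the visit: share = F / (T + F).
- From the last dose: share = (F − 4) / (T + F − 4).

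| Child | From last dose | From visit |
|---|---|---|
| Stops at Week 12 on IV | 12/24 = 50% | 16/28 = 57% |
| Stops at Week 24 on IV | 12/36 = 33% | 16/40 = 40% |
| Stops at Week 36 on SC | 8/44 = 18% | 12/48 = 25% |
| Completer, not entering AMAZ | 8/60 = 13% | 12/64 = 19% |

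A child who enters AMAZ has no follow-up window in this study, so the share is 0%.

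**Step 4. Scale of one case.** SAP 5.2 plans about 10 children above 40 kg and about 20 at or below. One uncounted child is 1/10 = 10 percentage points in a group of 10, 1/20 = 5 in a group of 20, and 1/30 = 3.3 overall.

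**The case against.** The best defence is that the plan makes an open and conventional choice. Protocol Appendix 1 defines a TEAE as emerging within a defined treatment period, and Protocol 10.2 and 10.3.1 assign safety analyses to induction and maintenance. On-treatment TEAE tables with a follow-up listing match that. This stands in full for TEAEs: leaving follow-up events out of those tables is not a defect.

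A reader might infer that SAP 6.13.3 contradicts Protocol 10.3.4. The documents do not support that. The sentence in 10.3.4 is general and sits within a section organized by period, so it supports adding a count but does not prove a conflict.

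A reader might also infer that follow-up deaths or SAEs are hidden. They are not: they are listed, and the registry summary may count them by group.

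It can also be said that SAP 6.13 leaves room for other statements, that footnote a to Table AMBU.6.1 allows further safety populations, and that the compound level safety standards, which are not among the documents, may specify follow-up outputs. That is fair. The visible text shows only that no such table is stated and that the default is a listing.

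Finally, with about 30 children, no planned treatment comparison and PK as the primary objective, a listing can be read case by case. It also shows context, such as a new therapy, that a table blurs. This limits the importance of the point but does not supply a count by dose group.

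**Conclusion.** The point holds for SAEs and deaths in the CSR. By the stated rule, a new event in follow-up is listed but enters no SAE number or percentage by dose group. The uncounted share of observed time runs from 13% to 19% for a completer outside AMAZ up to 50% to 57% for a child who stops at Week 12 on IV dosing.

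Those shares rest on the planned follow-up lengths and on the treatment period closing at the last treatment visit. A reader might take them as the fraction of SAEs missed. The documents give no event rate, early-stop rate or AMAZ rollover rate, so they support no forecast of missed events and no estimate of how many children are affected. Nothing is claimed about adverse events of special interest: by default they follow the same periods (SAP 6.13.7), but their detailed subsections are not visible.

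Severity is low. The trial is small and the events are already listed. The remaining reason to act is that a short addition gives a complete count and prevents an unexplained difference from the registry summary.

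**What to change.** Keep the on-treatment tables and the listings as they are. Add to SAP 6.13.3 one supplementary table:

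- Number and percentage of safety-population patients with death or any SAE, from first dose through last follow-up visit.
- Columns: the induction weight/treatment dose groups of Table AMBU.6.2 (5 mg/kg, 10 mg/kg, 300 mg) and All miri.
- A flag for events that start after another UC therapy begins, since Protocol Appendix 5 lets investigators use otherwise prohibited drugs after the early termination visit.
- A footnote for children escalated from 5 to 10 mg/kg at Week 12 (Protocol 5.1).
- Counts and percentages only. The exposure in SAP 6.13.1 ends with the treatment period and would be the wrong denominator for a rate.
- A sentence reconciling the table with the SAE count in SAP 6.18 and stating whether that summary includes follow-up.

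The cost is a few lines of SAP text and one small table on data already collected. The drawback is interpretive: follow-up length differs between children, and some events will occur on other therapy or after escalation, so they may not reflect the assigned dose. The flag and footnote show this, and the on-treatment table remains the main display.

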6.13.1. Extent of Exposure

Duration of exposure to study treatment will be summarized by weight/treatment dose groups for the Safety population in the combined Induction and Maintenance period. For the treatment period of interest associated with the safety analysis population, exposure will be calculated as (date of last study visit during the treatment period – date of first dose for the treatment period +1 day).

Total patient-years (PY) of exposure will be reported for each of the weight/treatment dose groups. Descriptive statistics (n, mean, SD, minimum, first quartile, median, third quartile, and maximum) will be provided for patient-weeks of exposure and the frequency of patients falling into different exposure ranges will be summarized. Exposure ranges will generally be reported in weeks using the following as a guide:

- >0, ≥4 weeks, ≥8 weeks, ≥12 weeks, ≥16 weeks, ≥24 weeks, ≥32 weeks, ≥40 weeks, ≥48 weeks
- >0 to <4 weeks, ≥ 4 weeks to <8 weeks, ≥ 8 weeks to <12 weeks, ≥ 12 weeks to <16 weeks, ..., >48 weeks

Additional exposure ranges may be considered if necessary.

6.13.2. Adverse Events

A treatment-emergent adverse event (TEAE) is defined as an event that first occurred or worsened in severity after baseline. The MedDRA Lowest Level Term (LLT) will be used in the treatment-emergent computation. The maximum severity for each LLT during the baseline period will be used as baseline. For events with a missing severity during the baseline period, it will be treated as 'mild' in severity for determining treatment-emergence. Events with a missing severity during the postbaseline periods will be treated as 'severe' and treatment-emergence will be determined by comparing to baseline severity. For events occurring on the day of first taking study medication, the start times of the study treatment and AE will be used to determine whether the event was pre- versus post-treatment. If start time for the AE is missing, it will be assumed to have started in the postbaseline period.

Summary tables of AEs to include the following:

- overview of AEs
- summary of TEAE Preferred Terms (PTs) by decreasing frequency
- summary of TEAE PTs by decreasing frequency within System Organ Class (SOC)
- summary of TEAE PTs by maximum severity by decreasing frequency within SOC
- summary of serious adverse event (SAE) PTs by decreasing frequency
- summary of AEs leading to study discontinuation, and

• listing of SAEs.

Summary tables will include the number and percentage of patients reporting an event. For events that are gender-specific (as defined by MedDRA), the number of participants at risk will include only patients from the given gender

The baseline period and postbaseline periods will be defined as follows:

- the baseline period is the Screening period, and
- the postbaseline periods will be a) the Induction period and b) the combined Induction and Maintenance period (see Table AMBU.6.2).

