5.1. Overall Design

Study AMBU is a multicenter, open-label PK study designed to evaluate the safety, PK, pharmacodynamics (PD), and clinical response of mirikizumab in pediatric patients, and to provide data for dose confirmation for Phase 3.

The study population includes patients with moderately to severely active UC who have an inadequate response to, loss of response to, or are intolerant to non-biologic therapy for UC (biologic-naive), and/or those who have been exposed to at least 1 biologic and/or JAK inhibitor therapy for UC (biologic/JAK inhibitor-experienced).

Patients weighing >40 kg will receive a mirikizumab induction dose of 300 mg via IV infusion and patients weighing ≤40 kg will receive induction doses of 5 or 10 mg/kg via IV infusion at Weeks 0, 4, and 8. Enrollment will begin with the 300 mg and 5 mg/kg dose cohorts. Patients in the 10 mg/kg cohort will be enrolled after 5 patients in the 5 mg/kg dose cohort have received 4 weeks of mirikizumab, an evaluation of the available PK in the 5 mg/kg cohort (as described in Section 10.3.8.1) has been conducted, and enrollment of the 5 mg/kg dose cohort has been filled.

Patients who achieve a Modified Mayo Score (MMS) clinical response (see Table AMBU.5) at Week 12 will proceed to the maintenance period and receive SC doses of 200 mg (weight >40 kg), or 100 mg (weight >20 kg to ≤40 kg), or 50 mg (weight ≤20 kg) mirikizumab Q4W through Week 48.

Patients who do not meet the MMS clinical response definition at Week 12 may receive extended IV induction dosing (either at the same dose or for the 5 mg/kg dose cohort, escalate to the 10 mg/kg dose) for 12 more weeks or discontinue. Following the completion of IV dosing at Week 24, if the investigator determines that the patient has improved, the patient will proceed to the maintenance period and receive Q4W SC doses based on weight class through Week 48. If the investigator determines that sufficient improvement was not made, the patient will discontinue study drug and undergo procedures for early termination of the study drug, including post-treatment follow-up as described in the Schedule of Activities (Section 2).

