5.2. Determination of Sample Size

Lilly plans to enroll approximately 30 patients into Study AMBU, to achieve at least 25 evaluable patients with respect to evaluating mirikizumab PK. The enrollment target includes approximately 10 patients in the >40 kg category and approximately 20 patients in the \le 40 kg category.

This sample size is considered adequate to evaluate the PK of mirikizumab treatment in pediatric patients.

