6.16.2. Interim Analyses

An interim analysis is planned when approximately 15 patients in the \leq 40 kg group reach Week 12. This analysis will allow confirmation of dose for patients \leq 40 kg to begin the Phase 3 study.

Interim analyses provided will include assessments and summaries of disposition, demographics, safety, PK, and efficacy endpoints. Safety analyses will include, but are not limited to summaries of exposure, AEs/SAEs, labs, vitals, AESIs, and immunogenicity and will be performed according as described in Section 6.13. Efficacy analyses will include summaries of MMS clinical remission, response, and the associated component scores at Week 12 and Week 52. Pediatric Ulcerative Colitis Activity Index remission, response, and associated scores will also be summarized at relevant visits. Refer to Section 6.10.1 for details regarding the analysis of each endpoint.

No multiplicity adjustment will be made due to multiple comparisons or due to interim analyses.

Additional data snapshots and/or interim analyses may be performed as deemed necessary, based on emerging data from the ongoing study.

Study sites will receive information about interim results ONLY if it is required for the safety of their patients.

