6.18. Clinical Trial Registry Analyses

Additional analyses will be performed for the purpose of fulfilling the Clinical Trial Registry (CTR) requirements.

Analyses provided for the CTR requirements include the following:

- Summary of AEs, provided as a dataset which will be converted to an XML file. Both Serious AEs and 'Other' AEs are summarized: by treatment/weight group and by MedDRA PT.
- An AE is considered 'Serious' whether or not it is a TEAE.
- An AE is considered in the 'Other' category if it is both a TEAE and is not serious. For each Serious AE and 'Other' AE, for each term and weight class, the following are provided:
 - o the number of participants at risk of an event
 - o the number of participants who experienced each event term
 - o the number of events experienced.

Consistent with www.ClinicalTrials.gov requirements, 'Other' AEs that occur in fewer than 5% of patients/subjects in every weight class may not be included if a 5% threshold is chosen (5% is the minimum threshold).

AE reporting is consistent with other document disclosures for example, the CSR, manuscripts, and so forth.

7. References

- [FDA] United States Food and Drug Administration. E9(R1) statistical principles for clinical trials: addendum: estimands and sensitivity analyses in clinical trials: guidance for industry. May 2021. Accessed August 08, 2022.
 - https://www.fda.gov/downloads/Drugs/GuidanceComplianceRegulatoryInformation/Guidances/UCM582738.pdf
- [ICH] International Council for Harmonisation. Addendum on estimands and sensitivity analysis in clinical trials. To the guideline on statistical principles for clinical trials. E9(R1). Adopted 20 November 2019. Accessed 09 August 2022. https://database.ich.org/sites/default/files/E9-R1 Step4 Guideline 2019 1203.pdf.

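### At the interim that supports the Phase 3 dose for patients ≤40 kg, crude adverse-event percentages favour 10 mg/kg in expectation because that cohort, by design, has been followed for less time

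*SAP*

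**What the plan says.** **How events are summarised.** SAP 6.13.2 states: "Summary tables will include the number and percentage of patients reporting an event". SAP 6.13.3 does the same for serious events and for events leading to discontinuation of treatment. The groups are those assigned. Protocol 10.3.4 adds event counts ("the number of treatment-emergent adverse events (TEAEs), as well as the number and percentage of patients who reported at least 1 TEAE"), and the registry output in SAP 6.18 also lists "the number of events experienced". None of these measures uses time at risk.

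**Periods.** In SAP 6.13.2, "the postbaseline periods will be a) the Induction period and b) the combined Induction and Maintenance period".

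**Exposure.** SAP 6.13.1 states: "Total patient-years (PY) of exposure will be reported for each of the weight/treatment dose groups". This is for the combined period only, and is not linked to the event tables.

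**Staggered cohorts.** Protocol 5.1 opens 10 mg/kg only after five 5 mg/kg patients have had 4 weeks of drug, the available PK has been evaluated, and "enrollment of the 5 mg/kg dose cohort has been filled".

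**Interim.** SAP 6.16.2 places it when about 15 patients ≤40 kg reach Week 12, to confirm their Phase 3 dose. "Safety analyses will include, but are not limited to summaries of exposure, AEs/SAEs, labs, vitals, AESIs, and immunogenicity", carried out as in Section 6.13.

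**Immature patients.** SAP 6.3 leaves patients who could not yet have reached a visit out of the analysis of that visit's endpoint, but keeps early discontinuers who would have reached it. Section 6.13 has no counterpart.

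**The concern.** A crude percentage of patients with an event rises with time observed. At the interim the 5 mg/kg patients all started before the 10 mg/kg patients, so in the combined-period table the two columns describe different lengths of follow-up. With no true difference between doses, the later cohort is expected to show the lower percentage. The direction is fixed by the enrolment rule and favours the higher dose.

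The Induction table is affected in a smaller way. The Safety population is everyone dosed at least once, so patients still within their first 12 weeks at the lock are in the denominator with only part of the period observed. Among patients ≤40 kg, sequential enrolment means these are mainly 10 mg/kg patients. The tables are descriptive, but they form part of the package for a paediatric Phase 3 dose decision.

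**Working it through.** The documents state no event rate, accrual rate or expected exposure, so there is no plan figure to reproduce. The following is an illustration.

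**Inputs from the documents:** about 20 patients ≤40 kg (SAP 5.2); lock when the 15th reaches Week 12 (SAP 6.16.2); 5 mg/kg filled first (Protocol 5.1); follow-up to Week 52.

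**Assumptions:** 5/10 mg/kg split 10/10 (range 8/12 to 12/8); even accrual of 0.5 to 4 patients per month; gap between cohorts of 0 or 8 weeks; the same constant hazard λ at both doses; 12-week risk 20% or 40%; no dropout.

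**Formulas:** λ = −ln(1 − 12-week risk)/12 per week. Follow-up t = min(52, lock − entry). Expected crude percentage = the mean over patients of 1 − exp(−λt). For the Induction table, t is capped at 12.

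**Worked case** (10/10, 1 per month, no gap, 20% risk):
- Spacing is 52/12 = 4.33 weeks. The 15th patient enters at 14 × 4.33 = 60.7 weeks, so the lock is at 72.7 weeks.
- 5 mg/kg follow-up is 52 (five patients), 51.0, 46.7, 42.3, 38.0 and 33.7 weeks: mean 47.2.
- 10 mg/kg follow-up is 29.3, 25.0, 20.7, 16.3, 12.0, 7.7 and 3.3 weeks: seven patients, mean 16.3. Two have not reached Week 12.
- λ = 0.0186 per week, or 0.97 per patient-year.
- Combined period: 58% against 25%. Induction: 20% against 17%.

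**Other accrual rates** (10/10, no gap, 20% risk; 5 against 10 mg/kg):

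| Patients/month | Mean weeks at lock | Combined period, % | Induction, % |
|---|---|---|---|
| 0.5 | 52.0 v 25.0 | 62 v 35 | 20 v 18 |
| 1 | 47.2 v 16.3 | 58 v 25 | 20 v 17 |
| 2 | 32.6 v 10.9 | 45 v 18 | 20 v 15 |
| 4 | 22.3 v 11.5 | 34 v 19 | 20 v 18 |

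Over all splits, gaps, accrual rates and both risks, the spurious difference is 15 to 50 points in the combined table and about 2 to 12 points in the Induction table. In the 10/10 case without a gap, 10 mg/kg would need a hazard about 2.0 to 4.5 times higher to show the same combined percentage as 5 mg/kg.

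**Restricted Induction table.** Limited to patients who could have reached Week 12 by the lock, it gives 20% v 20% (or 40% v 40%), so the artefact is zero. It then holds 15 − 10 = 5 patients on 10 mg/kg in the 10/10 case (7 with 8/12, 3 with 12/8).

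**Exposure-adjusted rates.** With a constant hazard both doses have the same expected rate: 0.97 per patient-year at 20% risk, 2.21 at 40%. If risk is front-loaded they mislead the other way. Assume an identical 20% risk in Weeks 0–12 and none later. Mean time to first event or Week 12 is 0.2/0.0186 = 10.8 weeks. Followed for 12 weeks, the rate is 0.2/(10.8/52) = 97 per 100 patient-years. Followed for 40 weeks, mean time at risk is 10.8 + 0.8 × 28 = 33.2 weeks and the rate is 0.2/(33.2/52) = 31.

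**The case against.** The strongest reply is that a near like-for-like table is already planned. Induction caps follow-up at 12 weeks, and it is where the assigned regimens differ: Week 12 responders in both cohorts move to the same weight-based SC doses. The Induction table removes most of the imbalance, and in a group of about 10 patients one patient is 10 points, close to the largest residual. This stands, and limits the point. It does not remove the residual, whose direction is known and which one sentence would eliminate.

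Nor does any document make a 5 against 10 mg/kg adverse-event contrast a decision criterion. SAP 6.2 says treatment comparisons are not planned, and the Protocol Synopsis bases Phase 3 dose confirmation on PK modelling. This also stands: the interim supplies safety by dose group as supporting information.

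Patient-years by dose group would show a reader that exposure is unequal. That helps only in part. A total in another table does not correct the percentages, and no Induction-only exposure is specified.

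The compound level safety standards may add exposure-adjusted displays. They are not among the documents, and the SAP text does not say that they do.

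A reader might infer that interim safety should simply rest on exposure-adjusted rates. The documents do not support that: Protocol 3.3 reports immediate hypersensitivity at the onset of or during infusion, so at least one known risk is tied to IV dosing, and the front-loaded example shows the bias reversing.

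**Conclusion.** The point holds for the interim, for the adverse-event and serious-adverse-event tables. Combined-period percentages favour 10 mg/kg in expectation by about 15 to 50 points with no true difference. The planned Induction table reduces this to about 2 to 12 points. Both ranges rest on the assumed accrual, split, gap, constant equal hazards and absence of dropout.

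Four stronger readings are not supported:
- That no comparable table exists. The Induction table is planned, and exposure is reported by group.
- That 10 mg/kg will look safer. This is a bias in expectation. With groups this small chance variation is large, and a truly higher hazard could offset it.
- That the final analysis has the same fault. All cohorts then have the same planned 52 weeks, and nothing in the documents indicates discontinuation differing by dose.
- That events of special interest are shown to lack adjustment. The text of those subsections is not available, and SAP 6.13.7 defers the displays to the compound level standards.

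A separate limit on the combined table is that 5 mg/kg nonresponders may receive 10 mg/kg in extended induction but are analysed as assigned, so their later events count under 5 mg/kg.

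**What to change.** **Main change.** In SAP 6.13.2, 6.13.3 and 6.16.2, state that at the interim any side-by-side reading of 5 and 10 mg/kg safety uses an Induction-period (Weeks 0–12) table limited to patients whose start date allowed Week 12 by database lock. This is the SAP 6.3 rule: early discontinuers who would have reached Week 12 stay in. All events in later-starting patients remain in the full Safety-population tables and listings, so nothing is hidden.

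**Supplement.** Add exposure-adjusted incidence rates to the combined-period tables, at least for any TEAE, SAEs and events leading to discontinuation: patients with an event per 100 patient-years to first event or end of period, with an exact Poisson 95% CI. Note beside them that they assume a constant rate, mix IV and SC time, and keep escalated 5 mg/kg nonresponders in the 5 mg/kg group.

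**Cost.** SAP wording and some programming. Time to first event must be derived, because SAP 6.13.1 computes only total exposure. The restricted table will hold few 10 mg/kg patients (3 to 7 under the assumed splits), and intervals will be wide. Trial conduct, dosing and sample size are unchanged.
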